Anterior cervical discectomy and fusion surgery (ACDF) is a common procedure performed by spine surgeons for degenerative disc disease and spinal stenosis of the cervical spine. Typically, patients present with neck pain associated with radiculopathy or myelopathy; ACDF surgery is the treatment of choice once conservative, non-operative therapies have been exhausted. During ACDF surgery, a discectomy is performed and an interbody spacer or cage is implanted in the disc space to facilitate arthrodesis and maintain stability and intervertebral height; this is further stabilized with plate and screws fixated at the intended level. There are many material and design options for interbody cages ranging from metal, plastic, composite, and allograft to enhance bone growth and optimize fusion. Polyetheretherketone (PEEK) and titanium are two materials commonly used to manufacture interbody cages and both are routinely utilized in ACDF surgery.¹ Although both PEEK and titanium cages are biocompatible with similar fusion rates (88% vs. 93% respectively³, 100% both cages⁸, and 100% vs. 86.5% respectively⁶), PEEK cages offer a modulus of elasticity similar to cortical bone, which can contribute to a lower subsidence rate by allocating stress and load.² However, given the smooth surface and hydrophobic properties of PEEK, it may inhibit cell adhesion and osseointegration.¹ Titanium cages offer durability and enhanced osseointegration but a higher modulus elasticity.⁴ There are other factors that can influence the performance of a cage aside from material, including endplate preparation, bone density, cage placement, and cage design⁹ Ideally, an interbody cage should possess biomechanical stability and biocompatibility with a low incidence of subsidence and a high potential for osseointegration while maintaining intervertebral height and alignment. In order to obtain some of these features there have been modifications in shape and structure of cages as well as the material surface (i.e. porous, roughened, or osteoconductive treated surfaces) to promote osseointegration.¹⁰ A recent technology growing in spinal surgery is the use of 3D printed titanium cages. 3D printing allows for the fabrication of atypical cage designs that traditionally could not have been manufactured.¹ These designs may include a more open and intricate structure to allow for significant bone packing and bone ingrowth. Another feature of 3D printing is the ability to modify the material surface to create an osteoconductive foundation.¹ 3D printed cages can incorporate these biomechanical factors to maximize the potential for fusion and stable fixation. In a preclinical study by McGilvray et al (2018), it was found that there was a significantly greater total bone volume within the 3D porous titanium device compared to PEEK at 8-weeks and 16-weeks as demonstrated on micro-CT as well as a significant decrease in flexion-extension range of motion for the 3D porous titanium device.¹ There are prior studies comparing traditionally manufactured titanium alloy cages to PEEK as cited in the previously mentioned fusion rates.^{3,6,8} In this pilot study proposal, a prospective, single-arm treatment group using a 3D printed porous titanium alloy cage (Spira™-C; Camber Spine Technologies, Wayne PA) will be compared to historical data based on literature review of fusion rates and patient reported outcomes of PEEK interbody cages .

OBJECTIVE

The objective of this study is to perform a prospective, single-arm clinical evaluation utilizing the Spira™-C 3-D printed titanium interbody device for treatment of degenerative disc disease and spinal stenosis of the cervical spine to evaluate fusion status and patient reported outcomes. The primary objective is fusion status; this will be measured using dynamic (flexion and extension) X-rays and CT scan at 12 months. Secondary objectives include evaluation of patient reported outcomes, VAS score (pain), NDI (neck disability index; pain and function), SF-36 (quality of life), and EAT-10 (dysphagia). Also, radiographs will be evaluated for the occurrence of device-related adverse events or complications, such as revision surgery at the index level, subsidence, migration, and failure or loosening of the interbody device. Neurological motor and sensory evaluations will be followed for improvement or worsening over the course of the study. Data collected from subjects treated with the Spira™-C Interbody Device will be compared to historical data based on literature review of fusion rates and patient reported outcomes of traditional PEEK interbody cages.

DESCRIPTION OF SPIRA™-C OPEN MATRIX CERVICAL INTERBODY DEVICE

The Spira™-C Open Matrix Cervical Interbody Device, manufactured by Camber Spine Technologies, was 510(k) cleared by the FDA on October 17, 2017. The Spira™-C device is a 3-D printed titanium alloy cage designed with open spiral supports to allow for a hollow chamber to facilitate the packing of bone graft to optimize fusion. Spira™-C is indicated for use at one or two contiguous levels from C3-C7 for degenerative disc disease (DDD) with up to grade I spondylolisthesis. It is intended to be used with a supplementary FDA-cleared plate fixation system. Spira™-C must be used with autograft or cancellous or cortico-cancellous allograft.

METHODOLOGY

Study Design

This is a post-market, single-arm, prospective clinical study to evaluate fusion status and patient reported outcomes using the Spira-C titanium interbody cage for degenerative disc disease where single-level ACDF surgery is indicated. The treatment group will consist of 40 subjects treated with the Spira™-C Interbody Device at one level. Patients with a diagnosis of cervical degenerative disc disease and/or spinal stenosis, radiculopathy or myelopathy and planning to undergo a 1-level ACDF surgery between C3-C7 will be screened. If the subject meets all of the inclusion criteria and none of the exclusion criteria, the patient will be approached regarding study participation by the surgeon or study coordinator. If the subject wishes to participate, the study coordinator will initiate the consent process. Once the consent process has been completed and the subject has signed an IRB approved informed consent form the medical history, cervical spine examination (motor/sensory), and baseline subject questionnaires (VAS, NDI, SF-36, and EAT-10) will be collected. Once the ACDF surgery has taken place as planned; data will be regarding the surgery performed, operative time, bone graft used, plate and screw fixation system used,

length of stay, and adverse events or complications related to the procedure, device, or cervical spine.

Subjects will be followed up postoperatively at 6-weeks, 3-months, 6-months, and 12-months as per standard of care, at the private practice or clinic. During these visits, subjects will complete the questionnaires, cervical spine (motor/sensory) examination completed by the investigator, and cervical spine x-rays done per standard of care. Adverse events related to the device and/or procedure and/or cervical spine will be assessed at each visit.

Radiographic assessments will be performed at all postoperative visits; fusion status will be measured using dynamic (flexion and extension) X-rays and CT scan at 12 months. Fusion status at 12-months will be evaluated by an independent spine surgeon. Radiographs, including a cervical spine CT at 12-months, will also be utilized to assess for device-related complications, including implant failure. Any clinically significant complications related to the device will be recorded as an adverse event. Specifically, subsidence, migration, and loosening of the device that result in non-union or pseudoarthrosis and/or clinically significant neurological symptomology will be considered a device failure and reported as an adverse event. Also, any incidental findings on the CT scan will be discussed with patient and a referral to primary care physician will be made for further evaluation if necessary.

Data collected from subjects treated with the Spira™-C Interbody Device will be compared to historical data based on literature review of PEEK cage fusion rates and patient reported outcomes.

This study design reflects the current standard of care for cervical degenerative disc disease and spinal stenosis with symptoms of radiculopathy or myelopathy. Anterior cervical discectomy and fusion using an interbody device with plate and screw fixation is the treatment of choice after conservative therapies (non-surgical, i.e., physical therapy, epidural steroid injections, pain medications) have been exhausted.

Study Population – Inclusion/Exclusion Criteria

Patients scheduled to undergo a primary single-level ACDF surgery between C3-C7 will be approached about potential study participation. If the patient wishes to proceed with study participation, the study coordinator will perform the informed consent process. After the consent process has been completed and study details have been discussed, the subject will be further screened for eligibility and given the subject questionnaires to complete.

Inclusion Criteria

1. ≥ 18 years of age and skeletally mature
2. Able to provide consent
3. Undergoing a primary, single-level ACDF between C3-C7
4. Diagnosis of symptomatic degenerative disc disease
5. Neck pain and/or radicular symptoms with a baseline Visual Analog Scale score of ≥ 4cm (0-10cm scale)
6. Baseline Neck Disability Index score of ≥ 20

7. Attempted at least 6-weeks of conservative non-operative treatment

Exclusion Criteria

1. Any prior history of cervical fusion
2. Requires cervical fusion of more than one level
3. Acute cervical spine trauma requiring immediate intervention
4. BMI > 40
5. Active systemic bacterial or fungal infection or infection at the operative site
6. History of vertebral fracture or osteoporotic fracture
7. Current treatment with chemotherapy, radiation, immunosuppression or chronic steroid therapy
8. History of osteoporosis, osteopenia, or osteomalacia that would contraindicate spinal surgery
9. Psychological or physical condition in the opinion of the investigator that would interfere with completing study participation including completion of patient reported outcomes
10. History of neurological condition in the opinion of the investigator that may affect cervical spine function and pain assessments
11. Subjects with a history of cancer must be disease free for at least 3 years; with the exception of squamous cell skin carcinoma
12. Pregnant, or plans on becoming pregnant
13. History of allergy to titanium

Intervention

The intervention will consist of 40 patients undergoing an anterior cervical discectomy and fusion surgery where the Spira™-C Open Matrix Cervical Interbody cage with autograft and allograft will be utilized for interbody fusion at a single-level between C3-C7.

Statistical Analysis

The primary objective of this pilot study is to evaluate fusion status using the Spira™-C titanium interbody device at the 12-months postoperative time point. Results obtained in this study will be compared to historical data based on literature review. Based on previous literature review, a sample size of 40 patients was determined to be adequate for this study. The Wilson Score method was used to calculate two-sided confidence intervals for a single proportion (fusion rate) from .70 to 1.00. A sample size of 40 produces a two-sided 95% confidence interval with a width equal to 0.274 when the sample proportion is 0.70 and 0.088 when the sample proportion is 1.00. The intervals may be wider based on dropout rate at the 12-month endpoint. Due to the pilot nature of this study, the dropout rate will help to provide an estimate for similar future studies.

Data and Safety Monitoring

The PI and study team (including sub-investigators, clinical research manager) will be responsible for data and safety monitoring. All adverse events will be reviewed to determine relatedness to the product and reported to sponsor as necessary (if related to product and unanticipated according to risk profile). The data will be reviewed for maintenance of confidentiality and integrity as well as the data collection process. The data and safety review will take place every six months from the date of the first patient enrolled into the study or after ten patients have been enrolled whichever comes first.

Adverse Events

Relevant adverse events (those related to the study device, the surgical procedure, or cervical spine) or complications will be recorded in this study; including revision surgery at the index level, pseudoarthrosis, subsidence, migration, and failure or loosening of the device. Subsidence, migration, or loosening of the device that result in non-union or pseudoarthrosis and/or clinically significant neurological symptomology will be considered a device failure and reported as an adverse event. Any unanticipated serious adverse events related to the device will be reported to the IRB as well as the manufacturer. Per Medical Device Reporting (MDR) regulation (21 CFR 803), manufacturers and facilities are required to report to the FDA when it is known that any of their devices have caused or contributed to a death or serious injury.

Protocol Deviations

The investigators are responsible for documenting all protocol deviations, including an explanation for why the deviation occurred. All protocol deviations will be recorded and submitted to the IRB per policy.

OUTCOMES

Primary Endpoint

- Successful cervical spinal fusion as measured by dynamic (flexion and extension) X-rays and CT scan at 12 months as evidence by the following three criteria: bony bridging, no development of pseudoarthrosis, and no presence of radiolucency

Secondary Endpoints

- Improvement in patient-reported outcomes as measured by VAS (≥ 2 -point improvement), NDI (≥ 15 -point improvement), SF-36 (≥ 15 -point improvement and EAT-10 (score of < 3) from baseline to 12-months.
- No occurrence of adverse events or complications related to the device by month 12; including revision surgery at the index level, subsidence, migration, and failure or loosening of the interbody device. Subsidence, migration, and failure that results

in non-union or pseudoarthrosis and/or clinically significant neurological symptomology will be considered a device failure and reported as an adverse event.

- No new or worsening neurological (motor and sensory of the cervical spine) deficit as compared to baseline through 12-months.

SUBJECT SCREENING AND ENROLLMENT

Patients scheduled to undergo a primary single-level ACDF surgery between C3-C7 will be approached about potential study participation. If the patient wishes to proceed with study participation, the study coordinator will perform the informed consent process. After the consent process has been completed and study details have been discussed, the subject will be further screened for eligibility and given the subject questionnaires to complete.

Screen Failures

If the subject does not meet all inclusion criteria or meets one of the exclusion criteria after signing consent, then the subject will be considered a screen failure and therefore, not enrolled into the study. The subject will also be considered a screen failure and not enrolled in the study if there is a change in surgical treatment based on the surgeon's observations and best practice intraoperatively.

Withdrawals

A subject who withdraws consent prior to study completion will be removed from the study and no longer followed. The surgery, instrumentation, and bone grafts are FDA approved and cleared and considered standard of care. The subjects may follow-up as needed and per standard of care at their own discretion if they decide to no longer participate in the study. The reasons for voluntary withdrawal or discontinuation of study subjects will be documented. If during the course of the clinical study, a study subject is non-responsive to attempts to schedule follow-up visits, communication methods such as phone calls, emails, mail, or other means as appropriate in an attempt schedule an appointment or determine if the subject has moved, died, or otherwise become lost to follow-up.

Study Synopsis

Sponsor	Camber Spine Technologies [name]
Protocol Version	Version 1.2 Date: 11.01.18
Study Title	A PROSPECTIVE CLINICAL PILOT STUDY OF FUSION RATES USING SPIRA™-C TITANIUM 3D PRINTED INTERBODY DEVICE FOR ANTERIOR CERVICAL DISCECTOMY AND FUSION (ACDF)
Site/ PI	Beaumont Health – Royal Oak (William Beaumont Hospital) Principal Investigator: [name]
Study Design	Post-market, single-arm, prospective clinical pilot outcomes study
Study Duration	Approximately 3 years (enrollment of first subject to the last follow-up visit)
Enrollment Number	Total: 40 Treatment: 40 Spira™-C Open Matrix Titanium interbody cage (on-label use)
Treatment Arm	40 patients undergoing an anterior cervical discectomy and fusion surgery where the Spira™-C Open Matrix Cervical Interbody cage with autograft and allograft will be utilized on-label for interbody fusion at a single-level between C3-C7.
	Data collected from subjects treated with the Spira™-C Interbody Device will be compared to historical data based on literature review of fusion rates and patient reported outcomes of traditional PEEK interbody cages.
Study Objectives	
Primary Objective:
 
 • To evaluate fusion status using the Spira™-C titanium interbody device for treatment of degenerative disc disease of the cervical spine at a single-level between C3-C7 at 12-months. 
Secondary Objectives:
 
 • To evaluate VAS, ODI, SF-36 and EAT-10 scores postoperatively compared to baseline/preoperative • To evaluate the occurrence of device-related or procedure related adverse events or complications including subsidence and pseudoarthrosis.

Study Endpoints	
Primary Endpoint:
 
 • Successful cervical spinal fusion as measured by dynamic (flexion and extension) X-rays and CT scan at 12 months and as evidenced by the following three criteria: bony bridging, no development of pseudoarthrosis, and no presence of radiolucency . 
Secondary Endpoints:
 
 • Improvement in patient-reported outcomes as measured by VAS (≥ 2-point improvement), NDI (≥ 15-point improvement), SF-36 (≥ 15-point improvement and EAT-10 (score of < 3) from baseline to 12-months. • No occurrence of adverse events related to the device by month 12; including revision surgery at the index level, subsidence, migration, and failure or loosening of the interbody device. Subsidence, migration, and loosening of the device that result in non-union or pseudoarthrosis and/or clinically significant neurological symptomology will be considered a device failure and reported as an adverse event. • No new or worsening neurological (motor and sensory of the cervical spine) deficit as compared to baseline through 12-months.
Inclusion Criteria	
A subject may be included if the following criteria are met:
 
 1. ≥ 18 years of age and skeletally mature 2. Able to provide consent 3. Undergoing a primary, single-level ACDF between C3-C7 4. Diagnosis of symptomatic degenerative disc disease 5. Neck pain and/or radicular symptoms with a baseline Visual Analog Scale score of ≥ 4 (0-10cm scale) for neck or arm pain 6. Baseline Neck Disability score ≥ 20 7. Attempted at least 6-weeks of conservative non-operative treatment
Exclusion Criteria	
A subject will be excluded if any of the following criteria are met:
 
 1. Any prior cervical fusion surgery 2. Requires cervical fusion of greater than one level 3. Acute cervical spine trauma requiring immediate intervention 4. BMI > 40 5. Active systemic bacterial or fungal infection or infection at operative site 6. History of an osteoporotic fracture and/or vertebral body fracture 7. Current treatment with chemotherapy, radiation, immunosuppression or chronic steroid therapy

	
 8. History of osteoporosis, osteopenia, or osteomalacia that would contraindicate spinal surgery 9. Psychological or physical condition in the opinion of the investigator that would interfere with study participation, including completion of patient reported outcomes 10. History of neurological condition in the opinion of the investigator that may affect cervical spine function and pain assessments 11. Subjects with a history of cancer must be disease free for at least 3 years; with the exception of squamous cell skin carcinoma 12. Pregnant, or plans on becoming pregnant 13. History of allergy to titanium

Study Schedule of Events
	
All subjects who sign an IRB approved consent form are considered in active screening to determine eligibility. Once a subject is consented, the following visits will take place:
 
Baseline Visit:
 
 • Medical history • Cervical Spine Exam • Demographics • VAS, NDI, SF-36, EAT 10 questionnaires • Cervical spine x-rays AP/lateral, flexion/extension or as done per standard of care 
Surgical Visit (≤ 60 days of baseline visit):
 
 • Surgery performed • Amount of Bone Graft, both local bone autograft/allograft used • Cervical plate and screw fixation system used • Adverse Events/Complications 
6-week Visit (± 2 weeks):
 
 • VAS, NDI, SF-36, EAT 10 • Cervical Spine Exam • Cervical AP/Lateral x-rays • Adverse Events 
3-month Visit (± 3 weeks):
 
 • VAS, NDI, SF-36, EAT 10, patient satisfaction questionnaires • Cervical Spine Exam • Cervical AP/Lateral and flexion/extension x-rays • Adverse Events 
6-month Visit (± 1 month):
 
 • VAS, NDI, SF-36, EAT 10 • Cervical Spine Exam • Cervical AP/Lateral and flexion/extension x-rays • Adverse Events

	
12-month Visit (\pm 2 months):
 
• VAS, NDI, SF-36, EAT 10• Cervical Spine Exam• Cervical AP/Lateral and flexion/extension x-rays• CT scan of the cervical spine without contrast• Adverse Events
--	---

REFERENCES

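### EAT-10 improvement from baseline is scored as a 12-month value below 3 with no baseline condition, so a subject who starts below 3 and does not change counts as improved

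*Combined protocol and SAP*

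**What the plan says.** The protocol (OUTCOMES, Secondary Endpoints) heads the endpoint "Improvement in patient-reported outcomes as measured by VAS" and continues with the other three instruments. VAS needs a gain of at least 2 points, and NDI and SF-36 at least 15 each. The last item has a different form: "EAT-10 (score of < 3) from baseline to 12-months". The Study Synopsis (Study Endpoints) scores it the same way.

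The synopsis objective is a comparison with the preoperative state: "SF-36 and EAT-10 scores postoperatively compared to baseline/preoperative". The data for that comparison are planned. Under Study Design, "baseline subject questionnaires (VAS, NDI, SF-36, and EAT-10) will be collected", and the Study Schedule of Events lists EAT-10 at baseline, 6 weeks, and 3, 6 and 12 months.

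Eligibility sets a floor for pain, "baseline Visual Analog Scale score of ≥ 4cm (0-10cm scale", and an NDI of at least 20. None of the 7 inclusion or 13 exclusion criteria sets a minimum EAT-10 or requires dysphagia. The Statistical Analysis section deals only with the fusion rate and gives no rule for EAT-10.

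**The concern.** The label and the objective promise a comparison with baseline, and the scoring rule makes none. VAS and NDI have entry floors as well as change criteria, so an improvement count means something for them. EAT-10 has neither, and the enrolled diagnosis is degenerative disc disease, so nothing in eligibility keeps the share starting below 3 small.

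The resulting rate mixes subjects who were below 3 before surgery with subjects who fell below 3 afterwards. One figure can come from no change, from new dysphagia offset by resolution elsewhere, or from real resolution. In a single-arm study the subject's own baseline is the only within-study reference, and this rule discards it. The protocol also plans to set its patient-reported outcomes against published PEEK results, so a rate labelled as improvement could enter that comparison although it need not reflect any improvement.

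**Working it through.** **1. The plan's own figure.** The only calculation in the document is the Wilson interval width for the fusion rate at n = 40. With z = 1.96 and z² = 3.841:

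- centre = (p + z²/2n) / (1 + z²/n)
- half-width = z·√[p(1−p)/n + z²/4n²] / (1 + z²/n)

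At p = 0.70 the centre is (0.70 + 0.0480)/1.0960 = 0.6825. The half-width is 1.96 × √(0.00525 + 0.00060)/1.0960 = 0.1368. The interval is 0.546 to 0.819, width 0.274. At p = 1.00 the interval is 0.912 to 1.000, width 0.088. Both match the Statistical Analysis section. The intervals below use the same method.

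**2. What the rule does to single subjects (hypothetical scores).**

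| Baseline | 12 months | Change | Counted as improved? |
|---|---|---|---|
| 0 | 0 | none | yes |
| 0 | 2 | 2 points worse | yes |
| 20 | 3 | 17 points better | no |

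With whole-number scores, the only worsenings that still count as improved are 0 to 1, 0 to 2 and 1 to 2, so at most 2 points.

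**3. The rate.** Let b be the share with baseline below 3, s the share of those still below 3 at 12 months, and r the share of the others who reach below 3. Then

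reported rate = b·s + (1 − b)·r

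If no score changes, s = 1 and r = 0, and the rate equals b. The document does not give b, so the values below are assumptions, with all 40 subjects measured at 12 months.

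| Assumed b | Counted as improved with no change | Wilson 95% interval |
|---|---|---|
| 30% | 12 of 40 | 18–45% |
| 50% | 20 of 40 | 35–65% |
| 70% | 28 of 40 | 55–82% |
| 90% | 36 of 40 | 77–96% |

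The rate equals the resolution rate r for every r only if b = 0, that is, if nobody starts below 3.

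**4. One rate, three histories.** Assumed counts, each giving 28 of 40 (70%):

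| Scenario | Below 3 at baseline | Rise to 3 or more | Others falling below 3 | Below 3 at 12 months |
|---|---|---|---|---|
| A | 28 | 0 of 28 | 0 of 12 | 28 |
| B | 28 | 6 of 28 (21%, 10–40%) | 6 of 12 (50%, 25–75%) | 28 − 6 + 6 = 28 |
| C | 12 | 0 of 12 | 16 of 28 (57%, 39–73%) | 12 + 16 = 28 |

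A is no change, B is new dysphagia offset by resolution, and C is resolution in more than half of those who started at 3 or more. The planned endpoint cannot tell them apart.

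**The case against.** The strongest reply is that the cut-off stands under the word improvement, so the sentence could mean improvement to a score below 3. On that reading 0 to 0 would not count, and the synopsis objective would support it. But the text does not contain those words, and the neighbouring items state points of improvement where EAT-10 does not. Even on that reading, a subject who starts at 0 could never respond, so results split by baseline would still be needed.

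Several other points stand in part:

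- No analysis of EAT-10 is specified, so a pooled rate is an inference from the endpoint wording. The planned PEEK comparison covers patient-reported outcomes in general and does not name an EAT-10 rate.
- The baseline shares and the three scenarios are assumed. Only the identity (no change gives a rate equal to b) follows from the document.
- A near miss such as 20 to 3 is a limit of any cut-off, and splitting by baseline does not cure it. That is why change scores are also requested.
- The protocol gives below 3 as a target and does not state that 3 or more is dysphagia. Reading a rise to 3 or more as new dysphagia is an inference from that cut-off.
- This is one of four instruments in a secondary endpoint of a 40-subject pilot, and the raw scores will exist. The data can be rescued later, but choosing the rule after seeing them invites selective reporting.

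**Conclusion.** The concern holds. As written, the EAT-10 component does not measure improvement from baseline, and it conflicts with its own heading and with the synopsis objective. This follows from the wording and needs no assumption. Its size depends on the share of subjects below 3 before surgery, which the document does not give. Over assumed shares of 30% to 90%, no change would read as 12 to 36 of 40 improved. Losses to follow-up would alter these counts, and the protocol states no dropout rate. The plan should be corrected, but the matter is confined to a secondary endpoint.

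**What to change.** Take EAT-10 out of the list of improvement criteria and name it as a status: EAT-10 below 3 at 12 months. Report it in two groups, each with its denominator and Wilson 95% interval:

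- baseline below 3: the share at 3 or more at 12 months (new dysphagia by the protocol's cut-off);
- baseline 3 or more: the share below 3 at 12 months (resolution).

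These groups do not register 0 to 2 or 20 to 3 as change. So also report the mean change from baseline with a 95% interval, and the numbers with a higher, equal and lower score than at baseline, at 6 weeks and at 3, 6 and 12 months. Make the same edit in OUTCOMES and in the Study Synopsis.

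The cost is revised endpoint wording and an added table, with no new data collection. The groups will be small: if 28 of 40 start below 3, resolution is estimated in 40 − 28 = 12 subjects, and 6 of 12 would carry an interval of 25–75%. The EAT-10 result may look less favourable than the pooled rate.

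### Does the device-complication secondary endpoint leave open whether symptom-free subsidence in a fused subject counts as an event?

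*Combined protocol and SAP*

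**What the plan says.** The endpoint appears twice in the combined protocol and SAP.

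- **Outcomes, Secondary Endpoints:** "No occurrence of adverse events or complications related to the device by month 12; including revision surgery at the index level, subsidence, migration", followed by failure or loosening of the cage.
- **Study Synopsis, Study Endpoints:** "No occurrence of adverse events related to the device by month 12; including revision surgery at the index level, subsidence, migration", with the same ending.

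In both places the next sentence says that such events, when they lead to non-union, pseudoarthrosis or clinically significant neurological symptoms, are a device failure and are reported as an adverse event. The Outcomes version of that sentence names failure where the Synopsis, Study Design and Adverse Events versions name loosening.

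Methodology, Study Design adds: "Any clinically significant complications related to the device will be recorded as an adverse event". It continues: "Specifically, subsidence, migration, and loosening of the device that result in non-union or pseudoarthrosis and/or clinically significant neurological symptomology" are device failures. It also says that radiographs, including the 12-month CT, "will also be utilized to assess for device-related complications, including implant failure". The only named independent reading is for the primary endpoint: "Fusion status at 12-months will be evaluated by an independent spine surgeon".

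On collection, Study Design gathers "adverse events or complications related to the procedure, device, or cervical spine" around surgery and then says: "Adverse events related to the device and/or procedure and/or cervical spine will be assessed at each visit". The Study Schedule of Events has the same split: adverse events and complications at the Surgical Visit, adverse events alone at the four follow-up visits. The Adverse Events section says that relevant adverse events or complications, with subsidence named, are recorded in the study.

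**The concern.** Take a subject who is fused and symptom-free at 12 months but whose cage has settled. If the endpoint counts complications, this subject fails it. If it counts only adverse events, and a complication becomes an adverse event only when clinically significant, the subject might pass. The Synopsis wording, the Study Design sentence on clinical significance and the follow-up visit lists all seem to point to the narrower count, while the Outcomes section points to the broader one.

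No measurement, threshold, reference image or reader for subsidence is given. The first scheduled film with the cage in place is at 6 weeks ± 2 weeks, that is weeks 4 to 8, so earlier settling has no scheduled reference. The worry is that the same images could yield success or failure, with the choice made after they have been seen. The background section raises the stakes: it links the lower modulus of PEEK to less subsidence and notes that titanium is stiffer.

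**Working it through.** **1. The plan's own figure.** Statistical Analysis gives two-sided 95% Wilson interval widths for the fusion rate at n = 40. With z = 1.96:

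- centre = (p + z²/2n) / (1 + z²/n)
- half-width = z·√(p(1−p)/n + z²/4n²) / (1 + z²/n)

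At p = 0.70 the limits are 0.5457 and 0.8193, width 0.2736 (stated 0.274). At p = 1.00 they are 0.9124 and 1.0000, width 0.0876 (stated 0.088). Both reproduce. They concern the primary endpoint and do not depend on the point at issue.

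**2. The two wordings side by side.**

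| Element | Outcomes | Synopsis |
|---|---|---|
| What is counted | adverse events or complications | adverse events |
| Listed items | index-level revision, subsidence, migration, failure or loosening | the same |
| Symptom condition on the list | none | none |
| Following sentence | labels events with consequences a device failure | the same, with loosening in place of failure |

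Subsidence is on both lists without a condition, so the difference in the opening words does not change how it is scored. The following sentence names a subset and how it is reported. It does not say that the rest of the list drops out. Study Design says that clinically significant complications become adverse events; it does not say that only those count for this endpoint. The Objective, the Synopsis objectives and the Adverse Events section also name subsidence without a symptom condition.

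**3. Are the data collected?** The schedule lists x-rays at all four follow-up visits and CT at 12 months. Study Design uses radiographs to look for device complications, and the Adverse Events section says complications are recorded. The shorter label on the follow-up lists does not remove them.

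**4. Size if the narrow reading were used.** Let a be the number of subjects whose only event is subsidence, migration or loosening without consequences. The two counts differ by a/40. Assume that all 40 are evaluable, that there are no other device events, and that the Wilson method is also used here (the plan states it only for fusion). The narrow count is then 40/40 throughout.

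| a | Broad count | Rate | 95% interval | Gap |
|---|---|---|---|---|
| 0 | 40/40 | 100% | 91.2 to 100.0% | 0 |
| 1 | 39/40 | 97.5% | 87.1 to 99.6% | 2.5 points |
| 2 | 38/40 | 95.0% | 83.5 to 98.6% | 5.0 points |
| 8 | 32/40 | 80.0% | 65.2 to 89.5% | 20.0 points |

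The first such subject lowers the lower limit by 91.2 − 87.1 = 4.1 points. The values of a are illustrations, since the documents give no subsidence rate.

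**The case for a change.** The strongest case for a change is that the tension lies inside each version rather than between them. An unqualified list is followed by a sentence that attaches adverse-event status to events with consequences, and Study Design reinforces this with its reference to clinical significance. The Synopsis, by dropping complications, makes the narrow reading easier. Even with the wording settled, two readers could classify the same films differently, because nothing says how much settling counts or who decides. Subsidence is a concern the protocol itself raises for a stiffer cage, and one clarifying sentence would cost little.

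Part of this stands. No sentence says outright that consequence-free subsidence counts, and the measurement convention is not written down. Failure and loosening are also interchanged in the device-failure sentence. But these are silences and a clerical slip; no stated rule has been shown to give a wrong result. The documents supply no threshold for subsidence, so any value would have to come from the sponsor. A perioperative reference image would depend on films the documents do not mention.

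The planned historical comparison, as described in the Objective, Study Design and Synopsis, covers fusion rates and patient-reported outcomes. Statistical Analysis speaks more loosely of comparing results, but gives no historical complication rate. No specified comparison turns on this count.

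**Conclusion.** The concern does not hold as a defect that requires a change. Device-related subsidence fails the endpoint under either wording on a plain reading, and device failure is a more serious subset within it. An analyst can follow that reading, tabulate all listed events and show device failures separately. Because complications are recorded and imaging is scheduled at every follow-up visit, a reader who prefers the narrower count can have that too.

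The missing measurement convention is a real gap in detail, of the kind usually filled in the image-reading instructions. It affects a descriptive secondary endpoint in a 40-subject pilot. The omitted reference to complications in the Synopsis, the shorter label at follow-up visits and the exchange of failure for loosening are editorial.

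Any difference is 2.5 points per subject scored differently, with all 40 evaluable; dropout would make each subject weigh slightly more. The total cannot be estimated from the documents and is zero if there are no consequence-free events. This conclusion rests on the Adverse Events section being followed, so that subsidence without symptoms is in fact recorded. The primary endpoint, its interval widths and the sample size stand as they are.
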